In the event of early study withdrawal or early discontinuation of the study intervention, all reasonable efforts should be made by the study personnel in-clinic or remotely to have the participants complete all study assessments of the EW Visit as per the schedule of activities.

Participants will be followed-up in-clinic or remotely for safety for 30 days after the last palovarotene dose of the study is received. If the study intervention was discontinued due to a safety concern, in the case of an adverse event (AE)/serious adverse event (SAE), the participant will be monitored until resolution, stabilisation or lost to follow-up and, in the case of pregnancy, the participant will be followed throughout the pregnancy and the health status of the baby verified up until one year of age.

An Independent Data Monitoring Committee will be set-up.

Intervention Groups and Duration:

This is a noncomparative rollover study.

Participants are eligible for the study whether they are receiving chronic or flare-up treatment in the parent study at the time of transition. Participants who previously interrupted/stopped palovarotene treatment and are currently under parent study follow-up are also eligible if they meet eligibility criteria. The dose of palovarotene administered will be individualised for each participant and based on the regimen (chronic or flare-up treatment), the dose received during their participation in the parent study at the time of transition to Study CLIN-60120-452 or prior to interrupting/stopping palovarotene treatment (to allow for dose modifications made to the standard chronic/flare-up regimen during the parent study).

Chronic/flare-up regimen:

Chronic treatment: oral palovarotene once daily, 5 mg, or at the dose received during participation in the parent study at the time of transition Study CLIN-60120-452 or prior to interrupting/stopping palovarotene treatment.

Flare-up treatment: increase in dose at the time of a flare-up (or substantial high risk traumatic event likely to lead to a flare-up) to 20 mg once daily for 4 weeks (28 days), followed by 10 mg once daily for 8 weeks (56 days) for a total of 12 weeks (84 days) even if symptoms resolve earlier.

Participants receiving flare-up treatment at the time of transition to Study CLIN-60120-452 will continue and complete the flare-up treatment as was planned in the parent study.

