2.2.3 Safety Profile of Palovarotene

Safety data from the FOP clinical studies reflect exposure to palovarotene in a total of 164 participants, including 139 participants aged 8 years and above for females and 10 years and above for males ($\geq 8/10$ years) for a mean duration of 94.1 weeks, to a maximum of 3.8 years. Participants received either:

- chronic/flare-up regimen: 5 mg daily dose of palovarotene with a 20/10 mg dose for 12 weeks at the time of flare-up (4 weeks of 20 mg once daily followed by 10 mg once daily for 8 weeks);
- flare-up regimen only: either the 20/10 mg dose for 12 weeks, a 10/5 mg dose for 6 weeks (10 mg once daily for 2 weeks followed by 5 mg once daily for 4 weeks) or a 5/2.5 mg dose for 6 weeks (5 mg once daily for 2 weeks followed by 2.5 mg once daily for 4 weeks).

In palovarotene-treated participants aged $\geq 8/10$ years, the most commonly reported adverse reactions were in the *Skin and subcutaneous disorders* (98.8%), *Gastrointestinal disorders* (86.6%) and *Infections and infestations* (82.3%) System Organ Classes (SOC). The majority of adverse events (AEs) were mild or moderate (19.5% and 56.7% of participants, respectively) across all palovarotene FOP studies.

Serious adverse reactions reported in palovarotene-treated participants aged $\geq 8/10$ years included PPC (preferred term (PT): epiphysis premature fusion) and cellulitis (13 participants each; 1.2%).

Adverse events leading to permanent discontinuation occurred in 9.8% of palovarotene-treated participants aged $\geq 8/10$ years. No study discontinuations were reported in placebo/untreated participants due to AEs. Mucocutaneous AEs leading to dose reductions were more common during palovarotene 20/10 mg flare-up treatment than during chronic treatment.

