Unit Dose Strength(s)	Each capsule contains 1 mg, 1.5 mg, 2.5 mg, 5 mg or 10 mg of palovarotene as active ingredient
Dosage Level(s)	
Chronic/flare-up regimen:
 
Chronic treatment 5 mg once daily (or at the dose received during participation in the parent study at the time of transition to Study CLIN-60120-452, or prior to interrupting/stopping palovarotene treatment)
 
Flare-up treatment 20 mg once daily for 4 weeks (28 days) 10 mg once daily for 8 weeks (56 days) Persistent flare-up symptoms: extension of 10 mg once daily in 4-week increments Intercurrent flare-ups (new flare-up location or marked worsening of original flare-up): 12-week flare-up treatment should be restarted
 
Chronic treatment: once daily, 5 mg or at the dose received during participation in the parent study at the time of transition to Study CLIN-60120-452 or prior to interrupting/stopping palovarotene treatment.
 
Flare-up treatment: increase in dose at the time of a flare-up (or substantial high risk traumatic event likely to lead to a flare-up) to 20 mg once daily for 4 weeks (28 days), followed by 10 mg once daily for 8 weeks (56 days) for a total of 12 weeks (84 days) (20/10 mg flare-up treatment) even if symptoms resolve earlier.
 
Flare-up treatment should begin at the onset of the first symptom indicative of a FOP flare-up or substantial high-risk traumatic event likely to lead to a flare-up. Symptoms of a FOP flare-up typically include but are not limited to localised pain, soft tissue swelling/inflammation, redness, warmth, decreased joint range of motion, and stiffness. Chronic treatment should cease at the time of initiation of flare-up treatment, re-initiation of the chronic daily treatment should occur after completion of the flare-up treatment.
 
Flare-ups can occur in the absence of any apparent causative factor, but there is a high risk that substantial traumatic events (e.g. surgery, intramuscular immunisation, mandibular blocks for dental work, muscle fatigue, blunt muscle trauma from bumps, bruises, falls or influenza-like viral illnesses), can lead to a flare-up and result in heterotopic bone formation. Flare-up treatment should be initiated at the time of such events.
 
Persistent flare-up symptoms: treatment may be extended in 4-week intervals with 10 mg palovarotene and continued until the flare-up symptoms resolve.
 
Intercurrent flare-up: if the participant experiences an intercurrent flare-up (new flare-up location or marked worsening of the original flare-up) at any time during the flare-up treatment, then the 12-week flare-up treatment should be restarted.
 
In the case of any intolerable adverse reactions, the daily dose of the chronic/flare-up regimen can be reduced (see Section 6.5).
 
Flare-up only regimen: If the participant experiences intolerable adverse reactions while taking chronic daily treatment and dose reduction does not alleviate the adverse reactions, then the participant may take palovarotene only at the time of flare-up (or substantial high-risk traumatic event).

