7.1.3 Treatment Interruption

Palovarotene can be temporarily discontinued if, after the daily dose of palovarotene has already been reduced to the lowest possible dose (see Section 6.5), the participant continues to experience intolerable adverse effects.

If palovarotene is temporarily interrupted, the participant will remain in the study and assessments performed as planned per the SoA.

If palovarotene is permanently discontinued, the participant will be withdrawn from the study and all reasonable efforts should be made by the study personnel to have the participant complete all study assessments of the EW Visit as per the SoA.

In case of suspected or confirmed COVID-19 (SARS-CoV-2) infection, the intervention administration may be temporarily discontinued depending on the participant clinical presentation. In some cases, the investigator may request a participant be retested before the intervention administration is resumed.

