Symptoms of a flare-up typically include, but are not limited to, localised pain, soft tissue swelling/inflammation, redness, warmth, decreased joint range of motion and stiffness. Only one symptom is required to define a flare-up. Flare-ups can occur in the absence of any apparent causative factor, but there is a high risk that substantial traumatic events (e.g. surgery, intramuscular immunisation, mandibular blocks for dental work, muscle fatigue, blunt muscle trauma from bumps, bruises, falls or influenza-like viral illnesses) can lead to a flare-up and result in heterotopic bone formation.

At each visit, the investigator will ask the participant if they experienced any flare-ups since their last visit, the location of the flare-ups, the start and stop date or whether it is ongoing, if any flare-up concomitant medication was taken and whether the flare-up resulted in extra bone growth and/or restricted movement. When extra bone growth occurred, the location will be specified and the investigators will ask the participant how the extra bone growth affected their movement.

Bone growth, loss of mobility and audiology impact that occurs as a consequence of a flare-up will be reported as an AE or SAE (see Section 10.3.1).

8.1.8 *Extra Bone Growth Assessment (without associated flare-up)*

For each extra bone growth (without associated flare-up) the location of the extra bone growth, whether it was preceded by injury, illness, vaccination and/or other events (“yes”, “no” or “unknown”), extra bone growth start date, duration and whether it is ongoing, will be collected at the Inclusion Visit and Follow-up/EOS/EW Visits.

At each visit, the investigator will ask the participant if they experienced any extra bone growth (without associated flare-up) since their last visit and the details of these extra bone growths.

8.1.9 *Qualitative Participant Interviews*

In-depth qualitative interviews will be proposed to all participants and will be conducted in person or by telephone by the PI/qualified site staff. Interviews can be carried out anytime within 1 year (ideally within 1 month) following the Inclusion Visit with consenting participants.

Participants will be asked to describe her/his past experience with FOP (e.g. symptoms, joint being locked) and with palovarotene (e.g. decrease in number of flare-ups, delay in physical disability, overall satisfaction).

Participants will also be asked to describe:

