### 5.7.2.2 Primary Analysis – Adverse Events

All adverse events (AEs) recorded in the eCRF will be coded using the latest version of MedDRA dictionary at the time of the database lock and will be classified by System Organ Class (SOC) and Preferred Term (PT). [Note: All ongoing AEs at the time of participant transition will be transferred from the parent study database]

AEs will be classified as Treatment-Emergent AEs (TEAEs) according to the rules below:

- Events with start date on or after the date of first IMP administration and up to 30 days after date of last dose of treatment of palovarotene in Study CLIN-60120-452 (or date of last contact if not available).

- Ongoing AEs from the parent study with a worsening in intensity or relationship (see relationship and intensity order below) to the study intervention following transition to Study CLIN-60120-452. New AEs during Study CLIN-60120-452 will be compared by SOC and PT to all previous study ongoing AEs for comparison of the intensity and relationship.

Ongoing AEs from the parent study with no change in intensity or relationship to the study intervention following transition to Study CLIN-60120-452 will therefore be an AE (non-TEAE).

In the case where it is not possible to define an AE as treatment emergent or not, the AE will be classified by the most conservative case; i.e. treatment emergent.

The below summaries will be provided:

- An overview table summarising the:
  - number and percentage of participants with at least one of the following AEs: any AE; any TEAE; maximum intensity of TEAEs; causality of TEAEs, worst causality and intensity of TEAEs (worst case); TEAE leading to a dose change; TEAE leading to withdrawal; TEAE leading to death; Serious Adverse Events (SAEs); Serious TEAE;
  - corresponding number of events for each of the AE categories listed above
- A summary of the number and percentage of participants reporting an AE by SOC and PT
- A summary of the number and percentage of participants reporting a TEAE by SOC and PT
- A summary of the number and percentage of participants reporting a TEAE by maximum intensity, SOC and PT
- A summary of the number and percentage of participants reporting a TEAE by worst causality, SOC and PT
- A summary of the number and percentage of participants reporting a related TEAE by SOC and PT
- A summary of the number and percentage of participants reporting a TEAE by intensity, causality, SOC and PT

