- A summary of the number and percentage of participants reporting a non-Serious TEAE by SOC and PT
- A summary of the number and percentage of participants reporting a non-Serious related TEAE by SOC and PT
- A summary of the number and percentage of participants reporting a TEAE leading to treatment discontinuation by SOC and PT
- A summary of the number and percentage of participants reporting a TEAE leading to dose change (increase or decrease) by SOC and PT

The below summaries will also be provided by treatment dose at time of AE onset (5mg, 10/20mg and all palovarotene):

- Overall summary of Adverse events
- A summary of the number and percentage of participants reporting a TEAE by SOC and PT

- A summary of the number and percentage of participants reporting a TEAE by maximum intensity, SOC and PT
- A summary of the number and percentage of participants reporting a TEAE by worst causality, SOC and PT
- A summary of the number and percentage of participants reporting a TEAE leading to treatment discontinuation by SOC and PT
- A summary of the number and percentage of participants reporting a TEAE leading to dose change (increase or decrease) by SOC and PT

To calculate the treatment regimen at time of AE onset, the start date of each AE will be merged with each participant dosing log. Given dosing end dates are not captured the latest dosing record prior to the AE start date will be identified. If the dosing record is either 0 mg or after treatment discontinuation the regimen will be set to “off treatment”.

AEs will be counted as follows:

- AEs summaries will be ordered in terms of decreasing frequency for SOC and PT within the overall column of each output.
- Participants with more than one AE within a particular SOC are counted only once for that SOC. Similarly, participants with more than one AE within a particular PT are counted only once for that PT.
- Participants reporting a TEAE more than once within that SOC/ PT, the TEAE with the worst-case intensity (intensity order: severe > missing > moderate > mild) will be used in the corresponding intensity summaries.
- Participants reporting a TEAE more than once within that SOC/ PT, the TEAE with the worst-case causality to study medication (order: related > missing > not related) will be used in the corresponding relationship summaries;

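### TEAEs leading to a dose increase and to a dose reduction share one overview row and one table, so the figure may not be readable as a tolerability rate

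*SAP*

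**What the plan says.** SAP 5.7.2.2 deals with dose change in three places:

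- The overview table has one row without direction, in the sequence "TEAE leading to a dose change; TEAE leading to withdrawal; TEAE leading to death".
- The SOC/PT outputs include "A summary of the number and percentage of participants reporting a TEAE leading to dose change (increase or decrease) by SOC and PT".
- The same table is repeated under the instruction "The below summaries will also be provided by treatment dose at time of AE onset (5mg, 10/20mg and all palovarotene").

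TEAEs leading to treatment discontinuation have their own tables and a listing, and all AE data are listed. Nothing is planned for reductions alone or for temporary interruptions alone.

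On dosing, Protocol 6.1 (Table 4) builds an increase into the regimen: "Flare-up treatment: increase in dose at the time of a flare-up (or substantial high risk traumatic event likely to lead to a flare-up"). An intercurrent flare-up restarts the course. Protocol 6.5 (Table 5) contains only downward steps, used for intolerable adverse reactions. Interruption is a separate pathway in Protocol 7.1.3: "If palovarotene is temporarily interrupted, the participant will remain in the study and assessments performed as planned per the SoA".

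**The concern.** The increase described in Protocol 6.1 is a response to disease activity or trauma. The decrease in Protocol 6.5 is a response to a drug reaction. One percentage covering both has no single interpretation.

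The sponsor's own summary of earlier studies reports reductions as a measure in their own right: "Mucocutaneous AEs leading to dose reductions were more common during palovarotene 20/10 mg flare-up treatment than during chronic treatment" (Protocol 2.2.3). A reader of the study report will want to know whether that pattern persists with longer exposure. The pooled overview row and table totals may not answer this, and an interruption could be counted in any of several places or in none.

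**Working it through.** The documents give no frequency for dose changes, so there is no planned figure to reproduce. The check compares the texts and then adds an illustration on assumed rates.

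**Can an escalation enter the table?** It must be attached to a TEAE with dose increase as the action taken.

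- Protocol 6.1 (Table 4) names surgery, falls, blunt trauma and influenza-like illness among the events that should start flare-up dosing. These could be recorded as AEs.
- Protocol 8.3.6, which would exempt disease-related events from AE reporting, is marked not applicable.
- The SAP names increase as one of the two directions, so it allows for such records.
- The available text does not say how the action taken is coded when flare-up dosing starts.

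Mixing is therefore plausible but not established.

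**Does the split by dose at onset recover direction?** No. From 5 mg, an event can lead up (flare-up dosing) or down (intolerance). From 10 mg, it can lead up (restart for an intercurrent flare-up) or down.

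**Illustration.** Let d be the share of participants with a TEAE leading to reduction and e the share with a TEAE recorded as leading to an increase. Both are assumptions. Under independence:

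pooled share = d + e − d·e

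share of pooled participants with a reduction = d ÷ pooled share

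With d = 10%, which is 0.10 × 87 = 8.7 participants at the maximum enrolment of 87:

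| e | Pooled share | Of these, with a reduction |
|---|---|---|
| 0% | 10% | 100% |
| 10% | 0.10 + 0.10 − 0.01 = 19% | 53% |
| 30% | 0.10 + 0.30 − 0.03 = 37% | 27% |
| 50% | 0.10 + 0.50 − 0.05 = 55% | 18% |

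With e fixed at 30% and d from 5% to 30%, the pooled share runs from 33.5% to 51% and the share with a reduction from 15% to 59%. Without independence, the pooled share lies between the larger of d and e and their sum. For 10% and 30% that is 30% to 40%.

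**By dose at onset.** Assume reductions of 10% at 5 mg and 20% at 10/20 mg, and AE-coded escalations of 30% and 5%. The pooled figures are 1 − 0.90 × 0.70 = 37% and 1 − 0.80 × 0.95 = 24%. Under these chosen values the totals would reverse the order of the reductions. This shows what could happen and is not a forecast.

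**Where would an interruption be counted?**

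- It is not named in the dose-change table.
- Protocol 6.5 and 7.1.3 describe temporary stops as a form of discontinuation, and the SAP overview has a separate withdrawal row. The treatment-discontinuation tables might therefore include them.
- SAP 5.7.2.2 also treats 0 mg as a dosing record, so an interruption might count as a decrease.

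The text allows each reading, and under none of them does a table isolate interruptions.

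**The case against.** The strongest reply is that the mixing is unproven. Flare-ups have their own assessment, flare-up dosing is taken from the dosing form, and the protocol's AE definitions (10.3.1) are not in the text available here. If no escalation is coded as AE-driven, e = 0 and pooling increases with decreases changes nothing. This stands, and it makes the point conditional.

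A reader might cite Protocol 8.1.7 as proof that escalations are counted: "Bone growth, loss of mobility and audiology impact that occurs as a consequence of a flare-up will be reported as an AE or SAE". It does not show that. Those AEs are consequences of a flare-up, whereas flare-up dosing starts at the first symptom, so they generally follow the escalation. The plausible route is through trauma or illness triggers.

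A reader might also infer that every fall in dose signals intolerance. It does not: the dose also falls by schedule, from 20 mg to 10 mg and then back to chronic dosing. Only an AE-driven decrease carries that meaning.

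It would also be too strong to say that the tolerability signal is lost. Mucocutaneous terms sit on different SOC/PT rows from falls or infections, so the contrast drawn in Protocol 2.2.3, which concerns mucocutaneous AEs only, remains largely readable on its own rows. Discontinuations are tabulated and listed, and all AE data are listed. The overview row and the table totals lack that protection.

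Finally, dose change is in neither the four primary endpoints nor the tabulations listed in Protocol 9.4.2. It is an SAP addition to a descriptive study. That limits the consequence, but the output still sits within the primary safety analysis and should be interpretable.

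**Conclusion.** The point holds in a limited form. SAP 5.7.2.2 pools the two directions in the overview row, the SOC/PT table and the table by dose at onset, and it plans no table that isolates reductions or temporary interruptions. Where trauma or illness triggers are recorded as TEAEs with dose increase as the action taken, the overview figure and totals are not a tolerability rate and the by-dose comparison is blurred.

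The size cannot be stated from the documents. It runs from zero upward, depending on coding that they do not describe, and every percentage in the working rests on assumed rates. The documents do not support a claim that the known pattern will be hidden or reversed, or that interruptions appear in no table. They may fall within an existing table, but none isolates them. The protocol-defined primary endpoints are unaffected.

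**What to change.** In SAP 5.7.2.2, replace the single dose-change category in the overview, the SOC/PT table and the by-dose-at-onset outputs with three: TEAEs leading to dose reduction, to temporary interruption (if collected) and to dose increase. Add two definitions: whether temporary stops count under treatment discontinuation, and how the action taken is coded when a flare-up or trauma starts or restarts flare-up dosing. Read the reduction category as the tolerability measure. Show interruptions beside it with their reasons, because Protocol 6.8 and 7.1.3 also allow stops for prohibited medicines and COVID-19.

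The cost is SAP wording, extra overview rows and about four more descriptive tables: one SOC/PT table becomes three and one by-dose table becomes three, so 2 + 2. No new visits or procedures are needed. The change depends on the CRF action-taken field distinguishing these categories, which the documents do not confirm. If it does not, the SAP should say what can be derived from the dosing records.
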